### **6.8.3 Grade 4**

For all Grade 4 laboratory-identified or clinical toxicities, TAF-FTC will be withheld unless it is determined to be not related. If a Grade 4 laboratory toxicity is not confirmed by repeat testing, it should be managed per algorithm for the new toxicity grade. Participants with Grade 4 AEs will be followed until the event resolves to baseline or stabilizes. Study drug may be restarted in the event of the resolution of a Grade 4 AE back to Grade 1, after consultation with the site investigator and other members of the PSRT. If the toxicity recurs to Grade 3 or higher after TAF-FTC is restarted and is considered to be related to TAF-FTC, the study medication will be permanently discontinued.

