#### **4.7 Toxicity Management**

Safety related laboratory testing will be performed at study entry and at week 8 and or as indicated by clinician during follow up. If enrollment occurs more 30 days after screening, entry safety labs will be repeated. These include HIV rapid testing, complete blood count, HBV surface antigen, serum creatinine, and urine pregnancy test. Toxicity will be managed in consultation with a clinician on the protocol. The clinician may discontinue the study drug at any time if he/she feels that continued use would be harmful to the participant. The PSRT should be consulted when possible. The PSRT will be consulted when considering further holding or recommencing study medication.

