## **6.8 Discontinuation of study drug with toxicity**

Grade I or II toxicity will be managed in consultation with a clinician on the protocol. The clinician may add follow up testing and evaluations, as medically indicated. Study drug can be continued except as noted below.

Grade III toxicities will be communicated to the PSRT and managed under the direction of a study physician. Follow up testing and evaluations will be added, as medically indicated. The toxicity will be evaluated for subject safety. If the adverse event may put the subject at increased risk, or jeopardizes the study's intent, even if not related with study drug, the subject will discontinue study drug. The PSRT will decide whether study drug can be restarted. If the adverse event is deemed not to be a significant health risk, the PSRT may recommend continuing study drug with close monitoring.

Grade IV toxicities will be communicated to the PSRT and managed under the direction of a study physician. If a grade IV event is related to the study drug, the participant will permanently discontinue the study drug and will be followed as medically indicated. If the grade IV is not related to the study drug, the PSRT will recommend whether study drug can be continued with close monitoring, or permanently/temporarily discontinued.

Participants who discontinue drug permanently due to a study drug-related AE will be followed until AE resolves or stabilizes and then the subject will be discontinued from the study.

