### **6.8.4 Creatinine Clearance**

Participants who enroll with a Grade 2 CrCl will discontinue study drug only if there is an increase in severity (to Grade 3 or 4). If the calculated creatinine clearance is  $<60\text{mL/min}$ , it should be confirmed ideally within approximately one week of the receipt of the results. Study drug should be halted temporarily awaiting confirmatory testing. The PSRT should be consulted for further guidance about restarting study drug for participants who fail to have a confirmed test within two weeks of receiving the initial result. If the calculated creatinine clearance is confirmed to be  $<60\text{ mL/min}$ , the study drug must be temporarily discontinued. The participant will be monitored as deemed clinically necessary in consultation with the PSRT until level returns to baseline (screening value) or stabilizes.

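### For a drug-related Grade 4 event, section 6.8 requires permanent discontinuation while section 6.8.3 allows a restart, and nothing says which rule governs

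*Combined protocol and SAP*

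**What the plan says.** Section 6.8 (Discontinuation of study drug with toxicity) splits Grade 4 events by relatedness. For related events: "If a grade IV event is related to the study drug, the participant will permanently discontinue the study drug". The PSRT has discretion only in the other branch: "If the grade IV is not related to the study drug, the PSRT will recommend whether study drug can be continued with close monitoring", or stopped temporarily or permanently.

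Section 6.8.3 (Grade 4) starts from a hold. For all Grade 4 toxicities, laboratory or clinical, "TAF-FTC will be withheld unless it is determined to be not related". A laboratory result that repeat testing does not confirm is managed at its new grade. Then comes the restart rule, "Study drug may be restarted in the event of the resolution of a Grade 4 AE back to Grade 1", conditional on being done "after consultation with the site investigator and other members of the PSRT". Permanent discontinuation appears once in 6.8.3, with this trigger: "If the toxicity recurs to Grade 3 or higher after TAF-FTC is restarted and is considered to be related to TAF-FTC".

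Section 4.7 (Toxicity Management) adds a general requirement: "The PSRT will be consulted when considering further holding or recommencing study medication". Section 8.13 (Study Discontinuation) only refers back to the permanent discontinuations for toxicity set out earlier.

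**The concern.** The two sections give different answers for the same participant: one whose Grade 4 event is confirmed, judged related to TAF-FTC, and later returns to Grade 1. Under 6.8 she never takes study drug again. Under 6.8.3 she may, once the PSRT has been consulted.

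What is at stake is re-exposure after the most severe related toxicity that section 6.8 addresses. The women are healthy, HIV-uninfected volunteers selected for low HIV risk (sections 3 and 3.1), so further drug offers them little personal benefit. Describing safety is the first primary objective (section 2.3). The PSRT needs to know whether a related Grade 4 event leaves it a decision to make: 6.8 says no, and 6.8.3 brings it the restart question.

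**Working it through.** No figure in the plan bears on this, so the check is a comparison of texts, plus one small count of missed doses.

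**Step 1. Outcome by relatedness, for a confirmed Grade 4 event that resolves to Grade 1**

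| Judgement | Section 6.8 | Section 6.8.3 |
|---|---|---|
| Related | Permanent stop; no PSRT option | Withheld; restart possible after PSRT consultation |
| Undetermined | Not addressed | Withheld; restart possible after PSRT consultation |
| Not related | PSRT recommends continuing, or a temporary or permanent stop | Need not be withheld |

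The first row is the conflict. The second row has a rule in 6.8.3 only. The third row is compatible.

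**Step 2. Does the 6.8.3 restart sentence reach related events?** It speaks of a Grade 4 event without qualification. The hold that precedes it exempts only events judged not related, so related events are among those held. Section 6.8.2 (AE Grade 3) follows the same pattern: hold if related, reintroduce at Grade 1 after consulting the PSRT, stop permanently on related recurrence. There the reintroduction plainly covers related events.

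**Step 3. Does another sentence set the order of precedence?**
- The words in 6.8 that defer to later text stand in the Grade I/II paragraph, not in the Grade IV paragraph.
- Section 4.7 requires PSRT consultation but does not say which rule the PSRT applies.
- Section 8.13 points back to the toxicity section.
- A rule that the specific overrides the general does not settle it. Both texts name Grade 4, and 6.8 is the more explicit on relatedness.

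None of these ranks the two rules.

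**Step 4. How often would it matter?** The documents give no Grade 4 rate, and section 8.5 calls the risk of serious side effects remote, so no probability can be derived from them. The missed-dose rules also narrow the case. Assume, since no recovery time is given, that return to Grade 1 takes at least one week. A one-week hold misses 1 × 2 = 2, 1 × 4 = 4 or 1 × 7 = 7 scheduled doses in the three arms. Each reaches the two consecutive missed doses at which section 3.8 replaces a participant. Section 8.13 gives two consecutive missed doses as an example of non-compliance for which the PI may discontinue her. Section 4.9 allows up to three sequential missed doses, for instance in an acute illness, and leaves anything further to the PSRT. None of these rules forbids a restart, but they remove most of the study's reason for one.

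**Step 5. Is the analysis affected?** Section 7.3.1 describes graded adverse events overall and by arm and compares proportions by chi-square. That plan is the same under either rule.

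**The case against.** The best defence is to read the sections together. Section 6.8 is mandatory and specific to related events; the 6.8.3 restart sentence is general and permissive. The restart sentence would still have work to do if confined to two other groups: events of undetermined relatedness, and unrelated events for which the PSRT recommended a temporary stop under 6.8. The recurrence clause also fits a first event that was not judged related. On this reading there is no conflict, and a site that never restarts after a related Grade 4 event complies with both sections.

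Part of this stands. The reading is available, and a cautious PSRT might adopt it. But the text does not compel it: the restart sentence carries no such limit, the hold it follows takes in related events, and the parallel Grade 3 rule allows reintroduction after a related event.

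The safeguard is also real. Sections 4.7 and 6.8.3 require PSRT consultation before a restart, and under 4.7 the clinician may stop drug at any time if continuing would be harmful. This limits the harm without telling the PSRT which rule to follow.

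A reader might also infer that 6.8.4 (Creatinine Clearance) repeats the conflict, because after a confirmed clearance below 60 mL/min "the study drug must be temporarily discontinued". It does not. Section 6.8.4 does not authorise a restart after a confirmed result, and the permanent stop in 6.8 can follow once the event is judged a related Grade 4.

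**Conclusion.** The inconsistency is real: 6.8.3 permits what 6.8 forbids for a confirmed, related Grade 4 event that resolves, and no sentence gives one of them precedence. This rests on the wording alone.

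Its practical reach is small. It needs a related Grade 4 event that returns to Grade 1 while dosing time remains in the 10 weeks, and a PSRT that does not object to restarting. Serious side effects are called remote, and a held participant would usually already be due for replacement, given the one-week recovery assumed above.

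Stronger conclusions are not supported. Sites are not forced to breach one section or the other, because the restart is optional. A site cannot resume drug without consulting the PSRT. The planned safety analysis is not compromised. This is an unclear participant-safety instruction that should be corrected because correction is cheap, not a flaw in the design or the statistics.

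**What to change.** In 6.8.3, replace the unrestricted restart sentence with a rule for each relatedness judgement, for example:

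> If a confirmed Grade 4 event is judged related to TAF-FTC, study drug is permanently discontinued (6.8) and is not restarted. If relatedness is undetermined, drug stays withheld and may be restarted only after resolution to Grade 1 and with PSRT agreement. If the event is judged not related, the PSRT recommends continuation, temporary or permanent discontinuation, or restart, as in 6.8.

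Keep the recurrence sentence. This applies the stricter of the two written rules to related events, gives undetermined events a rule, and leaves intact the PSRT discretion that 6.8 grants for unrelated events. Section 6.8.4 needs no change.

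If the sponsor does intend to allow rechallenge after a related Grade 4 event, amend the related-event sentence in 6.8 instead, so that one rule remains.

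The cost is a few sentences in a protocol amendment, with no added tests, visits or participants.

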### **6.8.4 Creatinine Clearance**

Participants who enroll with a Grade 2 CrCl will discontinue study drug only if there is an increase in severity (to Grade 3 or 4). If the calculated creatinine clearance is  $<60\text{mL/min}$ , it should be confirmed ideally within approximately one week of the receipt of the results. Study drug should be halted temporarily awaiting confirmatory testing. The PSRT should be consulted for further guidance about restarting study drug for participants who fail to have a confirmed test within two weeks of receiving the initial result. If the calculated creatinine clearance is confirmed to be  $<60\text{ mL/min}$ , the study drug must be temporarily discontinued. The participant will be monitored as deemed clinically necessary in consultation with the PSRT until level returns to baseline (screening value) or stabilizes.

## **6.9 Reporting Requirements for this Study**

For each study participant, the SAE/EAE reporting period begins at Enrollment (Day 0) and ends when the participant's follow-up in the study ends. All reportable SAEs occurring during the study reporting period will be reported to the principal investigator

### **6.10 Social Impact Reporting**

It is possible that participants' involvement in the study could become known to others, and that a social impact may result (i.e., because participants could be perceived as being HIV-infected or at risk or "high risk" for HIV infection). For example, participants could be treated unfairly, or could have problems being accepted by their families and/or communities. A social impact that is reported by the participant and judged by the IoR/designee to be serious or unexpected will be reported to the responsible site's IRBs at least annually, or according to their individual requirements. Social impacts will be collected and reported on CRFs during regular visits. In the event that a participant reports a social impact, every effort will be made by study staff to provide appropriate care and counseling to the participant as necessary, and/or referral to appropriate resources for the safety of the participant. The study site will provide such care and counseling in accordance with standardized guidance in the SSP Manual. While maintaining participant confidentiality, study site may engage their CAB in exploring the social context surrounding instances of social impacts, to minimize the potential occurrence of such an impact.

## **7 STATISTICAL CONSIDERATIONS**

### **7.1 Review of Study Design**

An open-label, randomized, three-arm, directly observed therapy, pharmacokinetic study. HIV-uninfected non-pregnant cisgender women will be randomly assigned 1:1:1 to 1 of 3 dosing frequencies of DOT TAF-FTC: 2, 4, or 7 doses/week to help differentiate poor and modest from perfect adherence. Drug concentrations in blood, cervico-vaginal fluid, and tissue will be measured during the study.

### **7.2 Study endpoints**

- **Aim 1:** Mean, variance, and dose proportionality for TFV-DP or TFV in plasma, DBS, and PBMC for 2, 4, 7 of DOT TAF-FTC dosing per week.
- **Aim 2:** Prediction model of adherence rate by level of TFV-DP in DBS.

## 7.3 Data Analysis

### 7.3.1 Primary outcomes

**Primary outcome 1:** The goal is to describe the frequency of adverse events, including emergent HIV infection during the study period. We will conduct a descriptive analysis for meeting PrEP157 eligibility among participants. The distribution of demographics and graded adverse events will characterize by overall and study arms and proportions will be compared between study arms using chi-square statistics.

**Primary outcome 2:** The goal is to quantify the effect of dose on steady state TFV-DP in DBS and PBMC based on an incomplete block design.  $C_{ss}$  (drug concentration at steady state) will likely require a normalizing log transform, such that geometric means and CIs will be reported. Dose proportionality will be assessed using the power model (on the natural log scale)  $\ln(Y_{ijk}) = \mu + S_i + P_j + \beta \log(D_k) + \varepsilon_{ijk}$  (Eqn. 1). Where  $Y_{ijk}$  is the response,  $C_{ss}$ , for the  $k$ th dose ( $k=2, 4, 7$  doses/week),  $j$ th period ( $j=1,2$ ),  $i$ th subject ( $i=1, \dots, 45$ );  $\mu$  is the overall mean,  $S_i$  is a random subject effect,  $P_j$  is the period effect and  $\varepsilon_{ijk}$  is random error. Dose proportionality dictates that  $\beta=1$  for dose-dependent parameters and we will assume dose proportionality if the 90% CI is contained within the limits (0.8, 1.25). The SAS mixed procedure will be utilized for model (Eqn 1), again assuming a random subject effect. Although we do not anticipate a period effect, our design allows us to test this effect. For the primary analysis, we assume no effect of 'non-daily dosing' regimens; although this will be examined in a secondary analysis. If dose proportionality is not shown, we will examine proportionality separately for each of the "non-daily dosing" dosing regimens. If dose proportionality is still not demonstrated when adherence regimens are examined separately we will consider dose as a categorical predictor.

In addition to the power model, we will utilize nonlinear mixed effects models using PK software (NONMEN and/or ADAPT-5) to model drug concentration over time on drug. For this analysis, all available drug concentration samples will be utilized, thereby accounting for missed doses due to protocol deviations. Change in objective function and/or AIC will be used to compare models. This approach will be used to further probe dose proportionality and the final model(s) will be used as a basis for simulation studies.

**Primary outcome 3:** The goal is to identify TFV-DP cut points associated with adherence levels. For the primary analyses, we will attempt to discriminate adherence for 2, 4 and 7 dosing based upon TFV-DP. As above, we will combine the "non-daily dosing" regimens. Linear mixed models with random intercepts, 25th percentiles, and receiver operating characteristics curves will be used to generate predicted concentration thresholds for varying dosing frequency (ranging from 1 to 7 doses/week) for each matrix-analyte pair. Analyses will be adjusted for age, contraception use, study arm, BMI, eGFR, and hematocrit.

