#### **5.1 Screening Procedures**

**Screening for COVID-19 symptoms and protection measures:** We will follow the standard of care of the Kenya Ministry of Health, KEMRI, and WHO guidelines on the COVID-19 virus. Participants will be informed about practicing good hand hygiene, masking, good respiratory hygiene, and maintaining social distancing. Staff will adhere to social procedures including maintaining a six foot distance and wearing masks. Unvaccinated participants and staff will be screened for COVID-19-related symptoms when they arrive at the clinic using a checklist to check for risk of COVID-19 exposure based on symptoms or contacts. Any person that comes to the clinic with symptoms consistent with COVID-19 that include 1 or more of fever, cough (dry or productive), dyspnea, or myalgias will be isolated. Participants will be educated about the Ministry of Health specified measures for seeking healthcare during this time. Referral

mechanisms to local public health facilities are in place. Finally, the clinical site will maintain a register of all visitors and participants who enter the study site, to support usual care contact tracing efforts where necessary.

At the screening visit a qualified study clinician will perform a history and physical exam for each participant. A complete medication history will be obtained including all drug allergies, immunization history, prescription, over the counter, and herbal treatments. Vital signs will include height, weight, blood pressure, pulse, respiratory rate and temperature. The following procedures will be conducted:

- Informed consent
- Safety Labs: Complete blood count (CBC, specifically hematocrit and hemoglobin), HBV surface antigen, serum creatinine)
- HIV antibody (rapid test or blood)
- Urine pregnancy test
- Medical, medication, vaccine history
- Physical exam

A screening test(s) may be repeated within the 30-day screening window. A participant who is unable to schedule a study entry visit within the 30-day screening window must be re-screened prior to entry into the study. Participants who have not been immunized for HBV will be offered vaccination, as per standard of care. An HBV Antibody test may be ordered for participants who are unsure of their vaccination history.

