#### 7.4 Sample Size Considerations

The overall sample size was chosen to have up to 18 cisgender women in each relevant group (overall, n=54 non-pregnant cisgender women) sufficient to provide precise information on drug concentrations and to balance feasibility, efficiency, and provide robust TAF/FTC data in DBS for cisgender women. The sample size for drug concentration parameters is based on ensuring precision in the estimates to accurately describe the concentration kinetics of TAF/FTC in non-pregnant cisgender women and is consistent with multiple DOT PrEP studies done in US populations. The precision desired is a mean TFV-DP in DBS at steady state within  $\pm 15\%$  of the true population mean. The mean ( $\pm$  standard deviation) TFV-DP at steady-state in HIV-uninfected US cisgender men and cisgender women following directly observed doses of 25 mg TAF/200mg FTC once daily for 12 weeks was  $2381 \pm 601$  fmol/punches [coefficient of variation (CV) of 25%] (*Anderson et al*). Based on this variability and assuming average TFV-DP results are normally distributed, to be 90% confident that the DBS TFV-DP sample mean is within 15% of the true mean, a sample size of 15 participants is required for non-pregnant cisgender women with conservative assumptions. With the planned enrollment of 18 cisgender women per group for this study, even a 10% non-completion rate at 8 weeks of DOT therapy, we provide ample data to estimate steady-state means to within 10% in cisgender women.

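### The primary dose-proportionality model compares different women across arms but includes no baseline covariates, so some precision on the deciding 90% CI may be lost

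*Combined protocol and SAP*

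**What the plan says.** **Design.** Section 7.1: "HIV-uninfected non-pregnant cisgender women will be randomly assigned 1:1:1 to 1 of 3 dosing frequencies of DOT TAF-FTC: 2, 4, or 7 doses/week". Section 7.4: "The overall sample size was chosen to have up to 18 cisgender women in each relevant group", 54 in total. Sections 2.5 and 7.5 agree: three parallel arms, one regimen per woman. Section 7.5 describes no stratification by body size, renal function or hematocrit.

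**Primary outcome 2 (Section 7.3.1).** "Dose proportionality will be assessed using the power model (on the natural log scale". Equation 1 sets log Css equal to a mean, a random subject effect, a period effect, beta times log dose, and error. "The SAS mixed procedure will be utilized for model (Eqn 1), again assuming a random subject effect". The decision rule is: "we will assume dose proportionality if the 90% CI is contained within the limits (0.8, 1.25". No covariate is listed. The model is introduced as "based on an incomplete block design", with two periods and 45 subjects.

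**Primary outcome 3 (same section).** "Analyses will be adjusted for age, contraception use, study arm, BMI, eGFR, and hematocrit". This sentence closes the outcome 3 paragraph.

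**Data at hand.** Section 5.1 takes hematocrit and hemoglobin (from the CBC) and serum creatinine at screening. "Vital signs will include height, weight, blood pressure, pulse, respiratory rate and temperature".

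**Covariates elsewhere.** Secondary objective 3 (Section 2.4) asks about the influence of variables such as hematocrit, age and weight. Section 7.3.2 item 3 pursues this with nonlinear mixed models and labels secondary analyses hypothesis-generating.

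**The concern.** A random subject effect removes between-woman variation from a dose comparison only if women receive more than one dose level. Here they do not, so all between-woman variation in steady-state concentration enters SE(beta), and through it the 90% CI that must fit inside 0.8 to 1.25. Covariates that predict concentration would take part of that variation out. The plan thinks them worth adjusting for in outcome 3 and gives no reason for omitting them in outcome 2.

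Two things are at stake. One is the width of the deciding interval, which matters most if a matrix is more variable than assumed or if beta is not exactly 1. The other is prespecification. If covariates are considered only after the data are seen, the analyst could choose which interval decides the question, and a failed criterion sets off the fallback sequence in Section 7.3.1.

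**Working it through.** **The plan's own figures.** Section 7.4 gives 2381 ± 601 for DBS TFV-DP on daily dosing. 601/2381 = 25.2%, which matches the stated CV of 25%. The stated n of 15 per group (mean within 15%, 90% confidence) is not reproduced by the simple formula: (1.645 × 0.252/0.15)² = 7.7, so 8, or 10 with t quantiles. The text cites conservative assumptions without naming them. That figure concerns the precision of a group mean and does not bear on this point. The plan states no power for the proportionality decision, so the following is new.

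**Inputs.**
- Doses 2, 4 and 7 per week; logs 0.693, 1.386 and 1.946; sum of squares about their mean Sxx = 0.788.
- n = 18 per arm, N = 54 (Section 7.4).
- sigma = √ln(1 + CV²) = √ln(1 + 0.252²) = 0.249.
- One Css per woman (assumption).
- R², the share of within-arm log-Css variance explained by the covariates: **not in the documents**; 0 to 0.3 shown.
- CVs of 35% and 50%: **assumptions**. The only CV given is 25%, for DBS; none is given for PBMC.

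**Unadjusted model.** SE(beta) = sigma/√(n × Sxx) = 0.249/√(18 × 0.788) = 0.066. With 52 df, t = 1.675 and the 90% half-width is 0.111. If beta = 1, the interval lies inside 0.8–1.25 with probability 0.89.

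**Adjusted model, p = 3.** Residual variance falls by the factor (1 − R²). Chance correlation between covariates and dose inflates the variance of beta by (N − 3)/(N − 3 − p) = 51/48 = 1.0625 on average. The SE ratio is therefore √(1.0625 × (1 − R²)):

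| R² | Calculation | Change in SE | Equivalent change in sample size |
|---|---|---|---|
| 0 | √1.0625 = 1.031 | +3% | −6% |
| 0.1 | √0.956 = 0.978 | −2% | +5% |
| 0.2 | √0.850 = 0.922 | −8% | +18% |
| 0.3 | √0.744 = 0.862 | −14% | +34% |

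The last column is 1/ratio² − 1. Break-even is R² = p/(N − 3) = 3/51 = 0.059; simulation of the fitted model places it at about 0.05–0.06.

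**Probability of meeting the criterion, beta = 1, 18 per arm** (simulation with 49 df after adjustment; good to about one percentage point):

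| CV | Unadjusted | R² = 0 | 0.1 | 0.2 | 0.3 |
|---|---|---|---|---|---|
| 25% (documented, DBS) | 0.89 | 0.87 | 0.91 | 0.94 | 0.96 |
| 35% (assumed) | 0.57 | 0.52 | 0.59 | 0.67 | 0.75 |
| 50% (assumed) | 0.11 | 0.08 | 0.14 | 0.22 | 0.31 |

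**Variations at CV 25%, R² = 0.1 / 0.2 / 0.3.** With beta = 0.95 and 18 per arm: 0.72 unadjusted; 0.74 / 0.78 / 0.83 adjusted. With beta = 1 and 16 per arm (10% non-completion, Section 7.4): 0.85 unadjusted; 0.86 / 0.90 / 0.94 adjusted.

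**The case against.** **The benefit is conditional.** No document reports an R². Section 3.1 restricts age to 18–30, eGFR to above 60 mL/min and hemoglobin to above 10 g/dL, so the covariates have a narrowed range and a low R² is plausible. Below about 0.05–0.06, adjustment costs precision. This stands, and it is why the point says precision may be lost.

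**At the documented CV the gain is modest.** The unadjusted model already passes with probability 0.89 when beta = 1. This also stands.

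**Bias.** A reader might infer that chance imbalance in body size or renal function distorts beta. It does not in the sense of bias: arms are randomised and the unadjusted 90% CI already allows for such imbalance.

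**Larger gains.** Scaling SE by √(1 − R²) alone would suggest savings of 5–16%, like enrolling 11–43% more women. That ignores the 51/48 inflation. Nor does the plan assert that BMI and eGFR determine concentration: it adjusts for them in outcome 3, and secondary objective 3 poses covariate influence as a question.

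**Covered elsewhere.** The nonlinear mixed models probe proportionality further and, as secondary work, examine covariates. They do not supply the interval in the decision rule. The outcome 3 adjustment sentence begins only with the word Analyses and might be meant to reach outcome 2. If so, the text should say so, and its list could not be used unchanged because study arm is the dose term.

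**A more basic defect.** Equation 1 describes two periods and 45 subjects, whereas the trial has 54 women in parallel arms. There is no second dosing period to estimate, and with one Css per woman the subject effect cannot be separated from error. That must be reconciled first; it does not remove the covariate question.

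**Conclusion.** The point holds as a matter of efficiency. The model whose 90% CI decides dose proportionality is a between-woman comparison with no baseline covariates, although suitable ones are collected in every woman and used in outcome 3. The size depends on an R² that the documents do not supply: from a 3% larger SE(beta) if the covariates predict nothing to a 14% smaller one at R² = 0.3. At CV 25% and beta = 1 that means about 2 points lost to about 7 points gained in the chance of meeting the criterion.

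The larger movements at CVs of 35% and 50% illustrate what happens if a matrix is noisier. They are not evidence that PBMC is that variable, and they do not show that the trial is underpowered for it. All figures assume one Css per woman, log-normal concentrations and covariates independent of randomised dose.

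**What to change.** In Section 7.3.1, primary outcome 2:

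1. Rewrite Equation 1 for the actual design: 54 women in parallel arms, no period term, and a subject effect only if repeated Css values per woman are modelled.
2. Add two or three prespecified linear terms measured before the first dose: weight or BMI (choose one), eGFR and, for DBS, hematocrit. Do not carry over the outcome 3 list. Study arm is the dose term, and a longer list raises break-even: six degrees of freedom would need R² above 6/51 = 0.12.
3. Name the adjusted beta and its 90% CI as the primary basis for the decision, with the unadjusted estimate as a sensitivity analysis.
4. State whether the adjustment sentence in outcome 3 applies to that outcome alone.

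The cost is wording; no new data are needed. The model spends 3 of 52 residual degrees of freedom. The downside, if the covariates prove not to be prognostic, is about 3% on SE(beta), or about 2 points of pass probability at CV 25%.
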